5.3 Duration of Therapy

In the absence of treatment delays due to adverse event(s), treatment may continue until one of the following criteria applies:

- Disease progression not meeting criteria dosing of study treatment beyond disease progression (see 5.3.1).
- Intercurrent illness that prevents further administration of treatment,
- Unacceptable adverse event(s), as defined in section 6.1.1, or at the discretion of the treating physician,
- Patient decides to withdraw from the study, or
- General or specific changes in the patient's condition render the patient unacceptable for further treatment in the judgment of the investigator.

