6. DOSING DELAYS/DOSE MODIFICATIONS

6.1 Atezolizumab

6.1.1 General AE Management and Dose Modification Guidelines

There will be no dose reduction for atezolizumab in this study.

Patients may temporarily suspend study treatment for up to 84 days (12 weeks) beyond the scheduled date of delayed infusion if study drug-related toxicity requiring dose suspension is experienced. If atezolizumab is held because of AEs for > 84 days beyond the scheduled date of infusion, the patient will be discontinued from atezolizumab and will be followed for safety and efficacy as specified in this protocol. If the AE resolves within 84 days and the patient is receiving corticosteroid therapy for the event, atezolizumab may be held for longer than 84 days (up to 4 weeks or for a total of 112 days) in order to allow tapering of the steroid dose to \leq 10 mg oral prednisone or equivalent.

Dose interruptions for reasons other than toxicity, such as surgical procedures, may be allowed for up to 84 days. The appropriate length of interruption will be at the discretion of the study PI in consultation with CTEP. Patients receiving surgery or other procedures for unequivocal progression of disease (for example, malignant bowel obstruction) must be permanently removed from study treatment.

Atezolizumab must be **permanently discontinued** if the patient experiences any of the following events, regardless of benefit:

- Grade 4 pneumonitis
- AST or ALT $> 5 \times$ ULN or total bilirubin $> 3 \times$ ULN
- Grade 4 diarrhea or colitis
- Grade 4 hypophysitis
- Any grade myasthenic syndrome/myasthenia gravis, Guillain-Barré or meningoencephalitis
- Grade 4 ocular inflammatory toxicity
- Grade 4 pancreatitis or any grade of recurrent pancreatitis
- Grade 4 rash
- Any grade myocarditis

Treatment may, under limited and compelling circumstances, be resumed in patients who have recovered from the following events, but only after consultation with the Study Principal Investigator:

- Grade 3 pneumonitis
- Grade 3 ocular inflammatory toxicity
- Grade 3 or 4 infusion-related reactions

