	Grade 2	
Hold atezolizumab.
 
Evaluate for alternative etiologies.
 
Initiate treatment as per institutional guidelines.
 
Resume atezolizumab if event resolves to grade 1 or better within 12 weeks.

AE Management and Dose Interruption Guidelines for Specific Toxicities in Treatment		
Toxicity	Severity/ Duration	Management
		Permanently discontinue atezolizumab if event does not resolve to grade 1 or better within 12 weeks.
	Grade 3 or 4	Permanently discontinue atezolizumab. Initiate treatment as per institutional guidelines.
Ocular event (e.g., uveitis, retinal events)	Grade 1	Continue atezolizumab. Patient referral to ophthalmologist is strongly recommended. Initiate treatment with topical corticosteroid eye drops and topical immunosuppressive therapy. If symptoms persist for more than 1 week, treat as a grade 2 event.
	Grade 2	Hold atezolizumab. Patient referral to ophthalmologist is strongly recommended. Initiate treatment with topical corticosteroid eye drops and topical immunosuppressive therapy. If event resolves to grade 1 or better within 12 weeks, taper corticosteroids and resume atezolizumab according to the guidelines above. Permanently discontinue atezolizumab if event does not resolve to grade 1 or better within 12 weeks.
	Grade 3 or 4	Permanently discontinue atezolizumab. Refer patient to ophthalmologist. Initiate treatment with 1–2 mg/kg/day oral prednisone or equivalent. If event resolves to grade 1 or better, taper corticosteroids over \geq 1 month. For grade 3 AEs, patient may only resume treatment after

AE Management and Dose Interruption Guidelines for Specific Toxicities in Treatment		
Toxicity	Severity/ Duration	Management
		
consultation with the trial PI; for grade 4, patient cannot resume treatment, regardless of benefit.

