Uveitis or episcleritis and other immune-mediated ocular disease may be associated with atezolizumab and may be treated with topical corticosteroid eye drops. Atezolizumab should be permanently discontinued for immune-mediated ocular disease that is unresponsive to local immunosuppressive therapy.

Serous retinopathy have been associated with cobimetinib.

Eye Toxicities	Management
Symptomatic eye toxicity (autoimmune uveitis, iritis or episcleritis)	
Hold atezolizumab and cobimetinib.
 
Consult ophthalmologist and start topical corticosteroid eye drops.
 
Consider starting prednisone 60 mg/day or equivalent.
 
Taper steroids over \geq 1 month once symptoms improve to Grade 0/1 (asymptomatic).
 
Atezolizumab may be restarted following resolution of the events with careful monitoring for recurrence.
 
Permanently discontinue atezolizumab for immune-mediated ocular disease that is unresponsive to immunosuppressive therapy.

Retinal vein occlusion Any grade	If RVO (any grade) is diagnosed, cobimetinib dosing should be permanently discontinued and RVO treated per institutional guidelines. Atezolizumab therapy may be continued.
Serous retinopathy Severity grade assessment based on NCI CTCAE v 5.0 “Eye Disorders – Other” scale. Grade 1: Asymptomatic or mild symptoms; clinical or diagnostic observations only; intervention not indicated	
Continue atezolizumab and cobimetinib without dose change.
 
Continue ophthalmology follow-up as clinically indicated.

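### For Arm B, the 6.3 eye row allows atezolizumab to restart after resolved uveitis at any grade without PI consultation, in conflict with 6.1.1 and 6.1.2

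*Combined protocol and SAP*

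**What the plan says.** Three places in the protocol govern atezolizumab after immune-mediated eye inflammation.

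- **Section 6.1.1** lists events after which atezolizumab must stop permanently, whatever the benefit. The list includes "Grade 4 ocular inflammatory toxicity". A second list names events after which treatment may resume in limited and compelling circumstances, but "only after consultation with the Study Principal Investigator". It includes "Grade 3 ocular inflammatory toxicity".
- **Section 6.1.2** has a table row headed "Ocular event (e.g., uveitis, retinal events". At Grade 3 or 4 it calls for permanent discontinuation. Resumption after Grade 3 needs consultation with the trial PI, and "for grade 4, patient cannot resume treatment, regardless of benefit".
- **Section 6.3**, under Potential Eye Toxicity, has a single ungraded row for symptomatic autoimmune uveitis, iritis or episcleritis. Both drugs are held, an ophthalmologist is consulted, topical steroid drops are started, prednisone 60 mg/day may be considered, and steroids are tapered over at least a month. Then "Atezolizumab may be restarted following resolution of the events with careful monitoring for recurrence". The row's only permanent stop is "Permanently discontinue atezolizumab for immune-mediated ocular disease that is unresponsive to immunosuppressive therapy".

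Section 6.2 tells sites treating combination patients to use 6.3 for adverse events of particular concern, and 6.2.1 and 6.1.1 for other events.

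**The concern.** The 6.3 row makes the permanent stop depend on response to treatment, while 6.1.1 and 6.1.2 make it depend on grade. A Grade 4 event that resolves is barred from re-treatment under the last two and eligible under the first. A Grade 3 event needs PI consultation under the last two and none under the first. The routing in 6.2, read literally, points an Arm B site to the more permissive text.

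What is at stake is patient safety. A patient could be re-exposed to atezolizumab after an event for which the protocol elsewhere forbids it. The scale printed in the same eye table for serous retinopathy describes Grade 4 as sight-threatening.

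**Working it through.** The check is mainly a comparison of texts. The plan gives no figure of its own on this point to reproduce.

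**1. Is it the same event?** Yes. The 6.1.2 row names uveitis, and section 7.3.4 gives uveitis as an example of ocular inflammatory toxicity, the term used in 6.1.1.

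**2. What does each text say for a resolved, symptomatic uveitis in Arm B?**

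| Grade | 6.1.1 | 6.1.2 ocular row | 6.3 eye row |
|---|---|---|---|
| 3 | Resume only in limited and compelling circumstances, after PI consultation | Discontinue; resume only after PI consultation | Restart allowed after resolution; no PI step |
| 4 | Permanent stop | Discontinue; no resumption | Restart allowed after resolution |

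**3. Which text prevails?** Section 6.2 routes listed events to 6.3. Against that, 6.1.1 uses *must* and is not limited to one arm, section 6.2.1 describes the 6.3 algorithms as suggested, and section 5.3 ends treatment for "Unacceptable adverse event(s), as defined in section 6.1.1, or at the discretion of the treating physician". These suggest that 6.1.1 is meant to bind in both arms. No sentence says so.

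**4. Is the omission deliberate?** Nothing indicates that it is. Within 6.3, the colitis, hepatic, rash and pulmonary tables all carry grade-based stops. The pulmonary table has both the Grade 3 PI step and the Grade 4 bar. Grade 4 serous retinopathy, in the same eye table, requires a permanent stop of both drugs. Section 6.3 is not uniform, however. Myocarditis of any grade is on the 6.1.1 stop list, yet the CPK table only asks sites to consider permanent discontinuation for clinically significant cardiac injury.

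**5. How wide is the gap?** Narrow. The paragraph above the eye table already calls for a permanent stop when immune-mediated eye disease does not respond to *local* immunosuppressive therapy. The row drops the word local. Under the lead-in, the gap shrinks to Grade 3 or 4 inflammation that resolves on local treatment, or that is given systemic prednisone together with the drops, so that failure of local therapy is never established.

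**6. How often could the question arise?** Section 7.1.1.1 lists uveitis and ocular inflammatory toxicity each as rare but serious, under 3%, with no split by grade. The inputs are:

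- Arm B: 82 / 2 = 41 patients, taking equal allocation from the planned 38 evaluable per arm (13.1, 13.2).
- Combined any-grade rate: 1% to 3% (assumed; the two terms overlap).
- Share that is Grade 3 or 4: 10% to 50% (assumed).

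Expected Grade 3 or 4 events in Arm B: 41 × 0.01 × 0.10 = 0.04, to 41 × 0.03 × 0.50 = 0.62.

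Chance of at least one: 1 − 0.999^41 = 4%, to 1 − 0.985^41 = 46%.

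This is the chance that such an event occurs at all. A wrongful restart also needs an event that resolves, a patient still suitable for treatment after the hold and taper, and a site that relies on 6.3 alone. The documents give no figure for any of these.

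**The case against.** The strongest reply is that a site can obey every text at once. Section 6.1.1 is mandatory, and 6.3 only says that atezolizumab may be restarted. A permission in a suggested algorithm does not cancel a bar. The routing sentence sits in the cobimetinib section and lifts nothing from the 6.1.1 list. On this view, silence in one row is weak evidence that the list is displaced, all the more because 6.3 is also loose in the CPK table.

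This is a reasonable reading and probably the intended one. It rests on inference, though. A site that follows 6.2 to the eye row finds a complete instruction with its own restart rule and no pointer back to 6.1.1.

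The second reply is that other safeguards exist. Ocular inflammatory toxicity must be reported within 24 hours (7.3.4), the primary study team including the PI meets weekly on adverse events (13.1), and prednisone must be down to 10 mg/day or less before atezolizumab resumes (6.1.2). These make it likely that the PI knows of the event. They do not require consultation before restart, and none states the Grade 4 bar.

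The third reply, that the lead-in's stop for failure of local therapy narrows the gap, is correct and is taken into account above.

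**Conclusion.** The concern holds in a limited form. The eye row conflicts with 6.1.1 and 6.1.2 at Grades 3 and 4, and the routing in 6.2 does not resolve the conflict. The row is wrong as written, and the severity is minor.

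A reader might infer more than the documents support:

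- **That 6.3 displaces the 6.1.1 list for Arm B, so re-treatment after Grade 4 is protocol policy.** The mandatory wording of 6.1.1 and the reference to it in 5.3 point the other way. What is missing is a statement of priority.
- **That this row is the only inconsistent place in 6.3.** The CPK table shows otherwise.
- **That 4% to 46% is the risk of harm.** It is the chance of any Grade 3 or 4 event in Arm B under assumed rates and severity shares. The chance of a wrongful restart is lower and cannot be estimated from the documents.
- **That the trial's result is affected.** With fewer than one such event expected in about 41 patients under these assumptions, there is no material effect on the comparison of progression-free survival.

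**What to change.** Three wording changes in section 6.3:

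1. Add one sentence: *The permanent-discontinuation and limited-resumption lists in 6.1.1 apply to both arms and override any more permissive text in 6.3.* This alone settles priority, and it also covers the CPK table.
2. Add two lines to the eye row: *Grade 3: stop atezolizumab permanently; resumption only in limited and compelling circumstances, after recovery and consultation with the trial PI. Grade 4: stop atezolizumab permanently, with no resumption whatever the benefit.* The Grade 3 line should keep discontinuation as the default and also keep the limited-circumstances condition. A bare PI-consultation line would be weaker than 6.1.1 and 6.1.2.
3. Insert *local* before immunosuppressive therapy in the row's non-response stop, so that it matches the lead-in.

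The hold, ophthalmology consultation, taper and resolution requirements stay as they are. The cost is a protocol wording amendment, with no new procedures, data or patients.

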
Symptomatic LVEF decrease from baseline
	
Withhold cobimetinib for up to 4 weeks; repeat LVEF
 
Resume at next lower dose if all of the following are present

	
 • Symptoms resolved, and • LVEF is at or above LLN, and • Absolute decrease from baseline LVEF is 10% or less 
Permanently discontinue if any of the following are present
 
 • Symptoms persist, or • LVEF is less than LLN, or • Absolute decrease from baseline LVEF is more than 10%
--	---

LVEF = left ventricular ejection fraction; LLN = lower limit of normal

Decreased LVEF may also result from immune related cardiomyopathy, a potential risk of atezolizumab therapy. For this reason, atezolizumab should also be held in the setting of decreased LVEF, pending the results of a cardiac workup. This work up should generally include troponin, CPK, cardiac MRI, EKG, and cardiology consultation. Atezolizumab may be restarted on a case-by-case basis as long as LVEF is $> 40\%$ (or $\leq 10\%$ absolute decrease from BL) and myocarditis has been excluded. For patients with more severe reductions in the LVEF, atezolizumab may be restarted only if the patient is clinically stable, and after consultation with the trial PI.

GUIDELINES FOR MANAGEMENT OF PATIENTS WHO EXPERIENCE ELEVATED CPK

Elevated CPK has been reported with cobimetinib. Recommended Dose Modifications for Cobimetinib in Patients with CPK Elevations are presented below.

Description	Management
CPK elevations	
Rule out cardiac cause (check ECG, serum cardiac troponin, and CPK-isoforms M and B fraction) and rule out rhabdomyolysis (clinical examination; serum creatinine, potassium, calcium, phosphorus, uric acid, and albumin; and urine myoglobin).
 
Consider permanent discontinuation of atezolizumab and cobimetinib if there is evidence of clinically significant cardiac injury or rhabdomyolysis. Assess patient for any history of strenuous physical activity, blunt trauma, or recent IM injections.

For Grade 3 CPK elevations that are asymptomatic and deemed not clinically significant	
Hold atezolizumab and cobimetinib pending workup to rule out immune related cardiomyopathy, myocarditis or other cardiac conditions. Workup should generally include ECG, serum cardiac troponin, and CPK-isoforms M and B fraction. Atezolizumab and cobimetinib may be restarted at previous dose and schedule only if cardiac etiology is ruled out.

	
Recheck CPK at least once a week. If CPK remains Grade 3 or decreases, continue cobimetinib at current dose and schedule.

For Grade 4 CPK elevations that are asymptomatic and deemed not clinically significant	
Hold atezolizumab and cobimetinib. Rule out immune-related cardiomyopathy, myocarditis or other cardiac conditions. Workup should generally include ECG, serum cardiac troponin, and CPK-isoforms M and B fraction.
 
Recheck CPK within 3 days. When CPK is Grade ≤ 3 and cardiac immune-related cardiomyopathy has been ruled out, atezolizumab and cobimetinib may be resumed with a dose reduction of cobimetinib by 1 dose level on the same schedule (e.g., 60 to 40 mg).
 
If Grade 4 CPK elevation recurs after 1 dose reduction, cobimetinib may be reduced by another dose level (e.g., 40 to 20 mg).
 
Permanently discontinue cobimetinib if Grade 4 CPK elevation recurs after 2 dose reductions of cobimetinib. Atezolizumab may be continued after consultation with the trial PI.

IM = intramuscular.

7. ADVERSE EVENTS: LIST AND REPORTING REQUIREMENTS

Adverse event (AE) monitoring and reporting is a routine part of every clinical trial. The following list of AEs (Section 7.1) and the characteristics of an observed AE (Sections 7.2 and 7.3) will determine whether the event requires expedited reporting via the CTEP Adverse Event Reporting System (CTEP-AERS) in addition to routine reporting.

7.1 Comprehensive Adverse Events and Potential Risks List(s) (CAEPRs)

The Comprehensive Adverse Event and Potential Risks list (CAEPR) provides a single list of reported and/or potential adverse events (AE) associated with an agent using a uniform presentation of events by body system. In addition to the comprehensive list, a subset of AEs, the Specific Protocol Exceptions to Expedited Reporting (SPEER), appears in a separate column and is identified with ***bold*** and *italicized* text. This subset of AEs (SPEER) is a list of events that are protocol-specific exceptions to expedited reporting to NCI (except as noted below). Refer to the 'CTEP, NCI Guidelines: Adverse Event Reporting Requirements' http://ctep.cancer.gov/protocolDevelopment/electronic_applications/docs/aeguidelines.pdf for further clarification.

NOTE: Report AEs on the SPEER **ONLY IF** they exceed the grade noted in parentheses next to the AE in the SPEER. If this CAEPR is part of a combination protocol using multiple investigational agents and has an AE listed on different SPEERs, use the lower of the grades to determine if expedited reporting is required.

7.1.1 CAEPRs for CTEP IND Agent(s)

7.1.1.1 CAEPR for Atezolizumab

Below is the CAEPR for Atezolizumab. Frequency is provided based on 3097 patients.

Version 2.3, March 11, 2021¹

Adverse Events with Possible Relationship to Atezolizumab (MPDL3280A) (CTCAE 5.0 Term) [n= 3097]			Specific Protocol Exceptions to Expedited Reporting (SPEER)
Likely (>20%)	Less Likely (<=20%)	Rare but Serious (<3%)	
BLOOD AND LYMPHATIC SYSTEM DISORDERS			
	Anemia		
CARDIAC DISORDERS			
		Heart failure ²	
		Myocarditis ²	
		Pericardial effusion ²	
		Pericardial tamponade ²	
		Pericarditis ²	
ENDOCRINE DISORDERS			
		Adrenal insufficiency ²	
		Endocrine disorders - Other (diabetes) ²	

Adverse Events with Possible Relationship to Atezolizumab (MPDL3280A) (CTCAE 5.0 Term) [n= 3097]			Specific Protocol Exceptions to Expedited Reporting (SPEER)
Likely (>20%)	Less Likely (<=20%)	Rare but Serious (<3%)	
	Hyperthyroidism ²		
		Hypophysitis ²	
	Hypothyroidism ²		
EYE DISORDERS			
		Eye disorders - Other (ocular inflammatory toxicity) ²	
		Uveitis ²	
GASTROINTESTINAL DISORDERS			
	Abdominal pain		Abdominal pain (Gr 2)
		Colitis ²	
	Diarrhea		Diarrhea (Gr 2)
	Dysphagia		
	Nausea		Nausea (Gr 2)
		Pancreatitis ²	
	Vomiting		Vomiting (Gr 2)
GENERAL DISORDERS AND ADMINISTRATION SITE CONDITIONS			
Fatigue			Fatigue (Gr 2)
	Fever ³		
	Flu like symptoms ³		
HEPATOBILIARY DISORDERS			
		Hepatic failure ²	
		Hepatobiliary disorders - Other (hepatitis) ²	
IMMUNE SYSTEM DISORDERS			
	Allergic reaction ³		
		Anaphylaxis ³	
		Cytokine release syndrome ³	
		Immune system disorders - Other (systemic immune activation) ²	
INFECTIONS AND INFESTATIONS			
Infection ⁴			
INJURY, POISONING AND PROCEDURAL COMPLICATIONS			
	Infusion related reaction ³		
INVESTIGATIONS			
	Alanine aminotransferase increased ²		
	Alkaline phosphatase increased ²		
	Aspartate aminotransferase increased ²		
	Blood bilirubin increased ²		
		Creatinine increased	
	GGT increased ²		
	Lipase increased*		
		Platelet count decreased	
		Serum amylase increased*	
METABOLISM AND NUTRITION DISORDERS			
	Anorexia		Anorexia (Gr 2)
		Hyperglycemia ²	

Adverse Events with Possible Relationship to Atezolizumab (MPDL3280A) (CTCAE 5.0 Term) [n= 3097]			Specific Protocol Exceptions to Expedited Reporting (SPEER)
Likely (>20%)	Less Likely (<=20%)	Rare but Serious (<3%)	
	Hypokalemia		
	Hyponatremia		
MUSCULOSKELETAL AND CONNECTIVE TISSUE DISORDERS			
	Arthralgia ²		
	Back pain		
		Generalized muscle weakness	
	Myalgia		
		Myositis ²	
NERVOUS SYSTEM DISORDERS			
		Ataxia ²	
		Encephalopathy ²	
		Nervous system disorders - Other (encephalitis non-infective) ²	
		Guillain-Barre syndrome ²	
		Nervous system disorders - Other (meningitis non-infective) ²	
		Myasthenia gravis ²	
		Paresthesia ²	
		Peripheral motor neuropathy ²	
		Peripheral sensory neuropathy ²	
RENAL AND URINARY DISORDERS			
		Acute kidney injury	
		Renal and urinary disorders - Other (nephritis) ²	
RESPIRATORY, THORACIC AND MEDIASTINAL DISORDERS			
	Cough		Cough (Gr 2)
	Dyspnea		
	Hypoxia		
	Nasal congestion		Nasal congestion (Gr 2)
		Pleural effusion ²	
		Pneumonitis ²	
SKIN AND SUBCUTANEOUS TISSUE DISORDERS			
		Bullous dermatitis ²	
		Erythema multiforme ²	
	Pruritus		
	Rash acneiform		
	Rash maculo-papular		
		Skin and subcutaneous tissue disorders - Other (drug reaction with eosinophilia and systemic symptoms [DRESS]) ²	
	Skin and subcutaneous tissue disorders - Other (lichen planus) ²		
		Skin and subcutaneous tissue disorders - Other (exanthematous pustulosis) ²	
		Stevens-Johnson syndrome ²	

Adverse Events with Possible Relationship to Atezolizumab (MPDL3280A) (CTCAE 5.0 Term) [n= 3097]			Specific Protocol Exceptions to Expedited Reporting (SPEER)
Likely (>20%)	Less Likely (<=20%)	Rare but Serious (<3%)	
		Toxic epidermal necrolysis ²	

*Denotes adverse events that are <3%.

¹This table will be updated as the toxicity profile of the agent is revised. Updates will be distributed to all Principal Investigators at the time of revision. The current version can be obtained by contacting [contact]. Your name, the name of the investigator, the protocol and the agent should be included in the e-mail.

²Atezolizumab, being a member of a class of agents involved in the inhibition of “immune checkpoints,” may result in severe and possibly fatal immune-mediated adverse events probably due to T-cell activation and proliferation. Immune-mediated adverse reactions have been reported in patients receiving atezolizumab. Adverse events potentially related to atezolizumab may be manifestations of immune-mediated adverse events. In clinical trials, most immune-mediated adverse reactions were reversible and managed with interruptions of atezolizumab, administration of corticosteroids and supportive care.

³Infusion reactions, including high-grade hypersensitivity reactions, anaphylaxis, and cytokine release syndrome, which have been observed following administration of atezolizumab, may manifest as fever, chills, shakes, itching, rash, hypertension or hypotension, or difficulty breathing during and immediately after administration of atezolizumab.

⁴Infection includes all 75 sites of infection under the INFECTIONS AND INFESTATIONS SOC.

Adverse events reported on atezolizumab (MPDL3280A) trials, but for which there is insufficient evidence to suggest that there was a reasonable possibility that atezolizumab (MPDL3280A) caused the adverse event:

BLOOD AND LYMPHATIC SYSTEM DISORDERS - Blood and lymphatic system disorders - Other (pancytopenia); Febrile neutropenia

CARDIAC DISORDERS - Cardiac arrest; Ventricular tachycardia

GASTROINTESTINAL DISORDERS - Constipation; Dry mouth; Ileus

GENERAL DISORDERS AND ADMINISTRATION SITE CONDITIONS - Chills; Edema limbs; Malaise; Multi-organ failure

HEPATOBILIARY DISORDERS - Portal vein thrombosis

INVESTIGATIONS - Lymphocyte count decreased; Neutrophil count decreased; Weight loss; White blood cell decreased

METABOLISM AND NUTRITION DISORDERS - Hypophosphatemia; Tumor lysis syndrome

MUSCULOSKELETAL AND CONNECTIVE TISSUE DISORDERS - Bone pain; Muscle cramp; Pain in extremity

NERVOUS SYSTEM DISORDERS - Headache

PSYCHIATRIC DISORDERS - Confusion; Insomnia; Suicide attempt

REPRODUCTIVE SYSTEM AND BREAST DISORDERS - Breast pain

RESPIRATORY, THORACIC AND MEDIASTINAL DISORDERS - Bronchopulmonary hemorrhage;

Pulmonary hypertension; Respiratory failure

SKIN AND SUBCUTANEOUS TISSUE DISORDERS - Alopecia; Dry skin²; Hyperhidrosis

VASCULAR DISORDERS - Hypertension; Hypotension; Thromboembolic event

Note: Atezolizumab (MPDL3280A) in combination with other agents could cause an exacerbation of any adverse event currently known to be caused by the other agent, or the combination may result in events never previously associated with either agent.

